### **Efficacy statistical methods:**

The investigator-assessed response will be assessed in Part 2 according to RAPNO criteria (MRI, neurological examination, and CSF cytology), as well as according to CSF cytology alone. The ORR and its 95% confidence intervals will be calculated using the Clopper-Pearson exact methodology.

The investigator-assessed DoR will be estimated using Kaplan-Meier methods. The median DoR and corresponding 95% confidence interval will be calculated.

PFS time will be estimated using Kaplan-Meier methods. The median PFS time as well as the proportion of patients without PFS events at 1 and 2 years post first dose will be estimated in Part 2, along with their respective 95% confidence intervals.

Estimates of OS at 1 year and 2 years post first dose will be made in Part 2 only using Kaplan-Meier methods.

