### 2.2.2.2. *Part 2*

- PK profile of Lu-DTPA-omburtamab in blood and CSF.
- Response, as defined by the RAPNO criteria (as determined from MRI assessments, neurological examination, and CSF cytology).
  - ORR, calculated as the proportion of all evaluable patients achieving a response (PR or CR) as best overall response at end of Cycle 1 and Cycle 3, EOT Visit, and at each Follow-up Visit.
- Investigator-assessed DoR, defined as the time from first response (CR or PR) to progression.
- PFS, defined as the time from first treatment to date of leptomeningeal progression or death from any cause, whichever comes first.
- OS defined as the time from first treatment to date of death.

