### 7.3.2. Response Evaluation, Overall Response Rate, and Duration of Response

Response, as defined by the RAPNO criteria (Warren et al. 2018; see Appendix 6) will be assessed in Part 1 at the EOT Visit. In Part 2, response will be assessed at end of Cycle 1 and Cycle 3, EOT Visit, then 26, 39, and 52 weeks post first dose, followed by 78 and 104 weeks post first dose of Lu-DTPA-omburtamab. Notably, objective response and stable disease requires that all criteria are met, while progression is defined when any of the PD criteria are met.

The ORR will be calculated from baseline MRI scans and from scans after the dosing of Lu-DTPA-omburtamab using 2 methods: firstly, by considering MRI data, neurological examination, and CSF cytology data together (RAPNO criteria); secondly, by considering CSF cytology data only. ORR will be defined as the proportion of all evaluable patients achieving a CR or PR as best overall response at the time of assessment.

Investigator-assessed DoR (Part 2) is defined as the time from response (CR or PR) to progression. Patients without any sign of progression will be censored at the date of their last PFS assessment.

In Part 1 and Part 2, the baseline CSF cytology assessment must be completed within 3 weeks prior to the first Lu-DTPA-omburtamab treatment dose infusion. Cerebrospinal fluid cytology should be assessed as positive/negative. Cerebrospinal fluid cytology will be assessed in Part 1 at screening, the EOT Visit, and in Part 2 at screening, end of Cycle 1 and Cycle 3, EOT Visit, and at each Follow-up Visit.

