### **8.4.1. Part 2 Efficacy Analysis**

Overall survival at 1 and 2 years post first dose will also be estimated using Kaplan-Meier methods. Patients not deceased will be censored at the last date known to be alive. The median PFS time and the proportion of patients without PFS events at 1 and 2 years post first dose will be estimated using Kaplan-Meier methods, along with their 95% confidence intervals. Results will be displayed in Kaplan-Meier plots. The ORR according to RAPNO criteria (MRI, neurological examination, and CSF cytology), as well as according to CSF cytology alone, will be assessed. The 95% confidence intervals will be calculated using the Clopper-Pearson exact methodology. Investigator-assessed DoR will be estimated using Kaplan-Meier methods. The median DoR and corresponding 95% confidence interval will be calculated.

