## Appendix 6: Assessment in Pediatric Neuro-oncology (RAPNO) Criteria

Response definitions: patients must meet **ALL** criteria in each response/stable disease category, or **ANY** criteria in the progressive disease category

	Complete Response (CR)	Partial Response (PR)	Stable Disease	Progressive Disease (PD)
Criteria	Must meet ALL criteria	Must meet ALL criteria	Must meet ALL criteria	Must meet ANY criteria
MRI-brain	Complete disappearance of all disease (enhancing and non-enhancing, measurable and nonmeasurable) for a minimum of 4 weeks; no new lesions	≥50% decrease (compared with baseline) in the sum of the products of perpendicular diameters of all (up to 4) measurable lesions sustained for at least 4 weeks; no progression of nonmeasurable disease	Does not meet criteria for CR, PR, or PD	≥25% increase (compared with smallest measurement at any timepoint) in the sum of the products of perpendicular diameters of all measurable lesions; significant progression of nonmeasurable disease not attributed to prior therapy; any new tumor (any new lesions suspected to be treatment related should be confirmed by biopsy)
MRI-spine	Complete disappearance of all disease (enhancing and non-enhancing, measurable and nonmeasurable) for a minimum of 4 weeks; no new lesions	≥50% decrease (compared with baseline) in the sum of the products of perpendicular diameters of all measurable lesions sustained for at least 4 weeks; no progression of nonmeasurable disease. If negative at baseline, must remain negative	Does not meet criteria for CR, PR, or PD	≥25% increase (compared with smallest tumor measurement at any timepoint) in the sum of the products of perpendicular diameters of all (up to 4) measurable lesions; significant progression of nonmeasurable disease not attributed to prior therapy; any new tumor (any new lesions suspected to be treatment related should be confirmed by biopsy)
CSF cytology	If tumor cells are present at baseline, must be negative × 2 (sampling at least 2 weeks apart)	If absent (negative) at baseline, must remain absent. If present at baseline, can be present or absent	If absent at baseline, must remain absent. If present at baseline, can be present or absent	Previously absent tumor cells in CSF now present (positive)
Neurologic exam a	Stable or improving	Stable or improving	Stable or improving	Clinical deterioration not attributable to other causes

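### The ORR by CSF cytology alone has no response rule of its own and is not limited to patients who are cytology-positive at baseline

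*Combined protocol and SAP*

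**What the plan says.** - Section 7.3.2 calculates ORR by two methods, full RAPNO and cytology only, and gives one definition for both: "secondly, by considering CSF cytology data only. ORR will be defined as the proportion of all evaluable patients achieving a CR or PR". It records cytology only as positive or negative.
- Section 8.4.1 repeats that ORR by RAPNO, "as well as according to CSF cytology alone, will be assessed", with Clopper-Pearson 95% intervals. The synopsis (efficacy statistical methods) also has "as well as according to CSF cytology alone". Neither adds a response rule.
- CR and PR are defined only in Appendix 6, which is a composite. Section 7.3.2 confirms that "objective response and stable disease requires that all criteria are met".
- The Appendix 6 cytology row reads, for PR, "If absent (negative) at baseline, must remain absent. If present at baseline, can be present or absent"; for stable disease, "If absent at baseline, must remain absent. If present at baseline, can be present or absent"; and for CR, "If tumor cells are present at baseline, must be negative" twice, on samples at least 2 weeks apart.
- Inclusion criterion 4 (Section 4.1) accepts patients in cytological remission, provided they are not also in radiographic remission.
- Sections 8.2 and 8.4 assign all efficacy endpoints to the FAS. Section 8.1 assumes that 20 of the 24 Part 2 patients are evaluable. No section defines evaluable.
- The secondary endpoint in Section 2.2.2.2 is "Response, as defined by the RAPNO criteria (as determined from MRI assessments, neurological examination, and CSF cytology"). The cytology-only rate is not listed there.

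**The concern.** In the composite it does no harm that the PR and stable disease cytology cells match, because the MRI rows separate the two categories. A cytology-only ORR removes the MRI rows, and the remaining row cannot tell a partial response from no change. Taken alone, its PR cell is met by a baseline-positive patient who never clears tumor cells and by a baseline-negative patient who stays negative.

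Reading the analysis as conversion from positive to negative is more natural, but leaves open who is counted. A baseline-negative patient cannot convert, and no section removes such patients from the denominator.

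At stake is whether the reported rate means anything definite. Part 2 is open-label and single-arm, and response is assessed by the investigator. If the rule is settled after the cytology results are known, the choice of rule can move the result.

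**Working it through.** **The plan's own figure.** The two-sided 95% Clopper-Pearson limits for x responders among n are the 0.025 quantile of Beta(x, n − x + 1) and the 0.975 quantile of Beta(x + 1, n − x). For 5/20 this gives 8.7% to 49.1%, which matches the 9% lower limit in Section 8.1. That figure is correct and is not affected by this point.

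**Inputs.** From the documents: 20 evaluable patients, binary cytology, the Appendix 6 cells and the interval method. Assumed, because the documents do not give them: 10 of 20 positive at baseline, 5 confirmed conversions, and no baseline-negative patient turning positive.

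**The same data under four readings.**

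| Reading | Count | ORR (95% CI) |
|---|---|---|
| Literal PR cell (extreme) | 10 positive + 10 negative that stay negative = 20/20 | 100% (83.2 to 100) |
| CR cell, baseline-negative patients meeting it by default | 5 + 10 = 15/20 | 75% (50.9 to 91.3) |
| Conversion over all evaluable | 5/20 | 25% (8.7 to 49.1) |
| Conversion over baseline-positive | 5/10 | 50% (18.7 to 81.3) |

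**No conversions at all.** The literal PR cell still gives 20/20 = 100%. The default-CR reading gives 10/20 = 50%. Conversion gives 0/20 (0 to 16.8) or 0/10 (0 to 30.8).

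**Dependence on the unknown baseline share.** Let P be the number positive among 20. With no conversions, the default-CR reading gives (20 − P)/20, which is 80% at P = 4 and 20% at P = 16. Conversion over all evaluable patients cannot exceed P/20, which is 20% at P = 4 and 80% at P = 16.

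**Denominator effect alone, at a constant 25% conversion rate.** Counting all 20 multiplies the rate by P/20.
- P = 16: 4/16 = 25% (7.3 to 52.4) against 4/20 = 20% (5.7 to 43.7).
- P = 4: 1/4 = 25% (0.6 to 80.6) against 1/20 = 5% (0.1 to 24.9).

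The dilution is therefore modest if most patients are positive at baseline and large if few are.

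**The case against.** The strongest reply is that nobody would lift the PR cell out of a composite that requires every row. Cytology is binary, so a cytological PR has no obvious meaning, and an analyst would count conversions. This largely stands. A reader might infer from the table that the plan would report a 100% response rate. The documents do not support that: Section 7.3.2 and Appendix 6 make the row one component among several. The 100% shows only that the row cannot serve alone. Even so, the stated rule is CR or PR, not conversion.

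Second, evaluable may be meant to cover only baseline-positive patients in this analysis. Nothing excludes that, so it would go too far to call the denominator wrong. It is unspecified. Against the restricted meaning, Section 8.1 uses the word for response in general, and Section 8.4 sends every efficacy endpoint to the FAS. The conflict between evaluable patients and the FAS also affects the RAPNO ORR. Only the baseline-negative problem and the missing response rule are specific to cytology.

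Third, dropping PR and counting unconfirmed patients as non-responders are choices that the documents do not compel. That is true. They are offered as the simplest rule built from text already in Appendix 6.

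**Conclusion.** The point holds as a minor one. The protocol plans a cytology-only ORR without a usable response rule and without limiting it to patients who can respond. Applied to the stated population, each available reading either counts unchanged cytology as a response or includes patients who cannot convert.

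In the illustration the same data run from 25% to 75% across the plausible readings, and to 100% at the literal extreme. Those figures rest on an assumed 10 of 20 positive at baseline, 5 conversions and no new positives. The denominator effect on its own can be small, as 20% against 25% with 16 positive shows.

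A reader might also infer that the trial's main ORR or its sample size is undermined. They are not: the listed endpoint is RAPNO response, and no test, threshold or sample-size statement uses the cytology-only rate. Confidence is high that the rule is missing. The size of the effect is uncertain because the baseline-positive share is not given.

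**What to change.** In Sections 7.3.2 and 8.4.1 and the synopsis:

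1. Define cytological response as positive at baseline and then negative on two samples at least 2 weeks apart (the existing Appendix 6 CR cell), with no PR category.
2. Use FAS patients who are cytology-positive at baseline as the denominator, count those without two confirming negatives as non-responders, and give the Clopper-Pearson interval.
3. Report baseline-negative patients separately, as the proportion remaining negative.
4. State whether a confirming sample counts if taken after new anti-cancer therapy, which Section 6.1 allows after the EOT Visit.
5. State whether cytology is part of the unscheduled 13-week visit for patients who stop after Cycle 1. Table 8, footnote 2, mentions MRI there but does not name cytology.

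The cost is a few sentences. Baseline and follow-up cytology are already scheduled, so the definition itself needs no new samples.

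There are two downsides. The denominator shrinks and the interval widens: in the illustration from 40.4 points (8.7 to 49.1) to 62.6 points (18.7 to 81.3). Confirmation may also come late, because Table 8, footnote 15, requires a repeat only of positive samples, so the second negative must come from a later visit. For a patient who stops after Cycle 1, the EOT Visit falls on Day 36 to 43, which is 7 to 14 days after the Day 29 sample. After Cycle 3 (dose on Day 71, sample on Day 99), it falls on Day 106 to 113, again 7 to 14 days later. Only the latest end of that range nominally reaches 2 weeks. Other patients would need a follow-up sample, and those without one would count as non-responders.

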### 7.3.3. Overall Survival (Part 2 Only)

The timeframe for assessment of OS will be from the first dose of Lu-DTPA-omburtamab to date of death from any cause. OS will be estimated using Kaplan-Meier methods.

## 7.4. Adverse Events

### 7.4.1. Definition of Adverse Events

An AE is any untoward medical occurrence in a patient administered a pharmaceutical product which does not necessarily have a causal relationship with the treatment.

An AE can therefore be any unfavorable and unintended sign (including an abnormal laboratory finding), symptom, or disease temporally associated with the use of a product, whether or not considered related to the product.

An AE includes:

- A clinically significant worsening of a concomitant illness.
- A clinical laboratory AE: a clinical laboratory abnormality which is clinically significant, i.e., an abnormality that suggests a disease and/or organ toxicity and is of a severity that

requires active management. Active management includes interventional treatment or further investigations, for example change of medicine dose or more frequent follow-up due to the abnormality.

A pre-existing condition (i.e., a disorder present before the AE reporting period started and noted on the medical history/physical examination form) should not be reported as an AE unless the condition worsens, or episodes increase in frequency during the AE reporting period.

Diagnostic and therapeutic non-invasive and invasive procedures, such as surgery, should not be reported as AEs. A medical condition for which an unscheduled procedure was performed should, however, be reported if it meets the definition of an AE. For example, an acute appendicitis should be reported as the AE and not the appendectomy.

#### 7.4.2. Definition of Serious Adverse Events

Each AE is to be classified by the investigator as either serious or non-serious. This classification of the seriousness of the AE determines the reporting procedures to be followed. An AE that meets 1 or more of the following criteria/outcomes is classified as serious:

- Is fatal or life threatening
- Requires inpatient hospitalization or prolongation of existing hospitalization
- Results in persistent or significant disability/incapacity
- Is a congenital anomaly/birth defect
- Is a medically important event.

 The term "life threatening" in the definition of "serious" refers to an event in which the patient, in view of either the investigator or sponsor, was at risk of death at the time of the event; it does not refer to an event that hypothetically might have caused death if it were more severe.

Death alone is not considered an AE; it is an outcome of an AE. Reports of death should be accompanied by the corresponding AE term for the event that led to death. However, sudden death or death due to unexplainable cause(s) should be reported as an SAE, while follow-up is pursued to determine the cause.

 Hospitalization is defined as admission to a hospital/inpatient (irrespective of the duration of physical stay) or is not admitted to a hospital/not an inpatient but stays at the hospital for treatment or observation for more than 24 hours. Events leading to hospitalizations for the following reasons should not be reported as SAEs:

- Trial-related purposes, not associated with any deterioration in condition
- Social reasons in the absence of any deterioration in the patient's general condition
- Elective surgery or other scheduled hospitalization periods that were planned before the patient was included in this trial.

 Medical and scientific judgment must be exercised in deciding whether an AE is believed to be "medically important". Medically important events may not be immediately life threatening or result in death or hospitalization but may jeopardize the patient or may require intervention to prevent one of the other outcomes listed in the definition above.

#### 7.4.3. Definition of Non-serious Adverse Events

A non-serious AE is any AE which does not fulfil the definition of an SAE.

#### 7.4.4. Definition of Adverse Events of Special Interest

The following AEs (serious and non-serious) are selected as Adverse Events of Special Interest (AESIs) and should be reported within 24 hours to the sponsor:

[figure not shown]
- Nervous system disorder Grade 3 and above (see [Section 7.1.5](#))
- Severe infections related to placement of intracerebroventricular device.
- Chemical meningitis (symptoms of clinical meningitis but cultures for infectious agents were negative) in which either: a) event is non-responsive to IV steroids, b) radiologic or operative intervention was indicated, or c) presence of focal neurologic deficit.
- Suspicion of liver injury, defined as:
  - ALT or AST  $>3 \times$  ULN and total bilirubin  $>2 \times$  ULN\* if baseline was within the normal reference ranges, or
  - ALT or AST increasing more than 3-fold from baseline value, if baseline was above normal reference ranges\*

\*Either criterion requires that no other reason can be found to explain the increased laboratory parameters, such as viral hepatitis A, B, or C, pre-existing liver disease, or another drug capable of causing the observed injury.

In cases of suspected liver injury, testing should be repeated within 48 to 72 hours for evaluation of the event course/confirmation. Furthermore, additional information needs to be provided by the site, such as physical examination, information on alcohol consumption, or concomitant therapy (including herbal medications). Aspects like abdominal pain/tenderness, nausea, vomiting, jaundice, fever, rash, hepatomegaly, splenomegaly, peripheral edema, and recent weight gain should be considered and described.

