### 4.1. Inclusion Criteria

Patients must satisfy all of the following criteria at the Screening Visit, unless otherwise stated:

1. Histologically confirmed diagnosis of medulloblastoma.
2. SHH, Group 3, or Group 4 according to World Health Organization 2016 classification.
3. Recurrent or refractory to frontline therapy, defined as:
  - a. For Part 1 only: Recurrent (maximum of 2 recurrences) or refractory to frontline therapy. Prior frontline or second-line therapy may involve surgery, craniospinal irradiation, stereotactic radiosurgery, and multi-agent chemotherapy regimens.
  - b. For Part 2 only: Recurrent (maximum of 1 recurrence) or refractory to frontline therapy. Patients with recurrent disease must have received second-line chemotherapy for progressive disease. Prior frontline or second-line therapy may involve surgery, craniospinal irradiation, stereotactic radiosurgery, and multi-agent chemotherapy regimens.
4. Have refractory disease, focal or multifocal recurrent disease, or pure leptomeningeal disease. Cytological or radiographic remission is allowed; however, not simultaneously.
5. Performance status score of 50 to 100, both inclusive, on the Lansky [ $<16$  years] or Karnofsky [ $\geq 16$  years] scales.
6. Aged 3 to 19 years, both inclusive, at the time of the first planned dose of trial treatment.
7. Life expectancy of at least 3 months, as judged by the investigator.
8. Acceptable hematological status prior to first dosing (hematological support is allowed if administered at least 1 week before administration of Lu-DTPA-omburtamab), defined as:
  - a. Hemoglobin  $\geq 8$  g/dL
  - b. White blood cell count  $\geq 1000/\mu\text{L}$
  - c. Absolute neutrophil count  $\geq 1000/\mu\text{L}$
  - d. Platelet count  $\geq 75\ 000/\mu\text{L}$ .

9. Acceptable liver function prior to first dosing, defined as:
  - a. Alanine aminotransferase (ALT) and aspartate aminotransferase (AST)  $\leq 5 \times$  upper limit of normal (ULN)
  - b. Bilirubin  $\leq 1.5 \times$  ULN.
10. Acceptable kidney function prior to first dosing, defined as:
  - a. Estimated glomerular filtration rate (eGFR)  $>60$  mL/min/1.73 m^2, calculated by the 2009 revised Bedside Schwartz Equation ([Appendix 4](#)).
11. Written informed consent from legal guardian(s) and/or child obtained in accordance with local regulations. Pediatric patients must provide assent as required by local regulations.

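### For children who enter with raised transaminases, the liver-injury AESI has no bilirubin trigger and an ALT/AST threshold of three times baseline that reaches 15 x ULN

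*Combined protocol and SAP*

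**What the plan says.** Section 7.4.4 lists events that "are selected as Adverse Events of Special Interest (AESIs) and should be reported within 24 hours to the sponsor". Suspicion of liver injury is one of them and has two alternative criteria:

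- ALT or AST above 3 x ULN and total bilirubin above 2 x ULN, "if baseline was within the normal reference ranges".
- "ALT or AST increasing more than 3-fold from baseline value, if baseline was above normal reference ranges".

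A footnote applies to both: "Either criterion requires that no other reason can be found to explain the increased laboratory parameters". Its examples include viral hepatitis, pre-existing liver disease and other drugs. A suspected case also calls for repeat testing within 48 to 72 hours and additional information from the site. AESIs are summarised separately under section 8.5.2.

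Section 4.1, inclusion criterion 9 ("Acceptable liver function prior to first dosing"), allows ALT and AST up to 5 x ULN and bilirubin up to 1.5 x ULN. Patients with raised baseline transaminases are therefore eligible by design.

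**The concern.** The two criteria are alternatives split by baseline, so each patient is covered by only one. In the raised-baseline group a bilirubin rise cannot trigger the AESI at any level, and the ALT/AST threshold grows with baseline and has no upper limit in multiples of ULN. The entry limits give no reason to drop bilirubin for this group: criterion 9 caps it at 1.5 x ULN for everyone, so a value above 2 x ULN lies above the entry limit for every eligible child.

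The AESI label carries the 24-hour report, the repeat testing and the place in the AESI table. A combined transaminase and bilirubin rise that falls outside the definition loses all three as AESI requirements. The liver is a poor organ in which to leave this gap. Table 1 gives it the highest predicted absorbed dose, 115.50 mGy/mCi in both sexes. Sections 1.3 and 3.3.3 name it as the one organ not predicted to receive a lower dose than with the iodine-131 product.

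**Working it through.** The documents state no derived figure on this point, so there is none to reproduce. The check is threshold arithmetic.

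Inputs:
- b = baseline ALT or AST in multiples of ULN; at most 5 (section 4.1, criterion 9a).
- Baseline bilirubin at most 1.5 x ULN (section 4.1, criterion 9b).
- Normal baseline: AESI if ALT or AST > 3 x ULN and bilirubin > 2 x ULN (section 7.4.4).
- Raised baseline (1 < b ≤ 5): AESI if ALT or AST > 3b x ULN, at any bilirubin (section 7.4.4).

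Baseline is read here as baseline ALT/AST.

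**Threshold by baseline (3 x b)**

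| Baseline ALT/AST (x ULN) | AESI threshold (x ULN) | Bilirubin |
|---|---|---|
| normal | > 3 | must also be > 2 x ULN |
| 1.5 | > 4.5 | not used |
| 2 | > 6 | not used |
| 3 | > 9 | not used |
| 3.33 | > 10 | not used |
| 4 | > 12 | not used |
| 5 (entry limit) | > 15 | not used |

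A child can exceed 10 x ULN without meeting the criterion only if 3b > 10, that is, if b > 10/3 = 3.33.

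**Cases with raised bilirubin**
- Baseline 4, ALT 11, bilirubin 3 x ULN: 11/4 = 2.75, below 3, so not an AESI. The same values after a normal baseline: 11 > 3 and 3 > 2, so an AESI.
- Baseline 2, ALT 5.9, bilirubin 3 x ULN: 5.9/2 = 2.95, below 3, so not an AESI. The same values after a normal baseline: 5.9 > 3 and 3 > 2, so an AESI.

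**Cases without a bilirubin rise**
- Baseline 1.2, ALT 3.7 x ULN, normal bilirubin: 3.7/1.2 = 3.08, above 3, so an AESI.
- Normal baseline, ALT 20 x ULN, normal bilirubin: not an AESI, because the bilirubin half is not met.

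The gap is therefore specific to combined rises. For isolated transaminase rises the raised-baseline criterion is the more sensitive of the two.

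**The case against.** Five points can be made on the other side.

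1. A reader might infer that the liver AESI is generally weaker in children who start with abnormal values. The documents do not support that. A normal-baseline child never qualifies on transaminases alone, while a child starting at 4 x ULN qualifies above 12 x ULN at any bilirubin. The point is confined to combined rises.

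2. The word baseline in the first criterion is not tied to an analyte, and it follows directly after the bilirubin limit. If it means baseline bilirubin, a child with raised ALT but normal baseline bilirubin falls under the combined criterion, and the 4 x to 11 x ULN case is flagged. This reading cannot be excluded. The second criterion, written in parallel, concerns only ALT and AST, which makes the transaminase reading likelier. The wording is also silent on mixed baselines, with one transaminase raised and the other normal.

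3. A reader might infer that a missed case goes unreported. It need not. It can be a serious adverse event if judged medically important (section 7.4.2), or a dose-limiting toxicity in Part 1 within 5 weeks of the first administration in Cycle 1 (section 3.1.1.2); both carry 24-hour reporting. Adverse events in Part 1 Cycle 1 are to be entered in the eCRF within 24 hours (Appendix 2), and all treatment-emergent events are tabulated. This narrows the gap without closing it. The serious-event route rests on investigator judgment. The dose-limiting route exempts Grade 3 laboratory values considered not clinically significant, if self-limiting and soon resolved, and has no counterpart in Part 2, where up to five cycles are allowed. Neither route puts the case in the AESI table.

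4. The footnote may exclude some children who enter at 4 to 5 x ULN because of pre-existing liver disease. That is so, but it applies to both criteria and supplies no trigger for the others.

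5. Applying the combined criterion to everyone without qualification would be non-specific. A child whose ALT falls from 4 x to 3.2 x ULN while bilirubin moves from 1.5 x to 2.1 x ULN would count as suspected liver injury. This objection stands, and the fix allows for it.

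**Conclusion.** The point holds as a gap in a safety-reporting definition, and it is minor. On the likelier reading of baseline, a bilirubin rise cannot trigger the liver-injury AESI in a patient with raised baseline transaminases, and the ALT/AST threshold is three times baseline, reaching 15 x ULN at the entry limit. Combined rises that would be AESIs after a normal baseline are missed at modest baselines (2 x to 5.9 x ULN) and at high ones (4 x to 11 x ULN).

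A reader might infer that any eligible child with raised values could pass 10 x ULN unflagged. That holds only for baselines above 3.33 and up to 5 x ULN. The documents do not say how many patients will have raised baseline transaminases, so the number affected cannot be estimated; planned enrolment is up to 25 in Part 1 and about 24 in Part 2.

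No primary endpoint is defined by the AESI. What is at stake is 24-hour reporting that does not depend on judgment, the linked repeat testing, and completeness of the AESI summary, mainly in Part 1 Cycle 2 and Part 2. If baseline in the first criterion means bilirubin, the gap narrows and the remaining defect is chiefly unclear wording.

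**What to change.** Reconcile the reporting definition in section 7.4.4 with the entry limits in section 4.1:

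- State which analyte baseline refers to in each criterion, and how mixed baselines are handled.
- Extend the protocol's own combined criterion (ALT or AST above 3 x ULN with total bilirubin above 2 x ULN) to raised-baseline patients whose ALT or AST has risen above their own baseline.
- Keep the more than 3-fold rise as an additional trigger.

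No event now flagged would be lost. Both missed cases in the working would be captured (11 > 4 and 5.9 > 2, with bilirubin at 3 x ULN). The falling-ALT case would not be, because 3.2 < 4.

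The change is about one line in section 7.4.4, plus the matching AESI derivation for the section 8.5.2 tables. The running cost is a few more 24-hour reports and repeat tests. Some specificity is lost in patients who enter above 3 x ULN: they already meet the transaminase half at entry, so a small further rise together with the bilirubin rise is enough.
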